8.4. Visit Procedure Description

8.4.1. General Procedures

The study will consist of 4 study visits over approximately 12 weeks. Subjects are expected to attend all study visits.

Written informed consent will be obtained for each subject before any study-specific assessments are performed. To ensure subjects have adequate time to evaluate and provide informed consent to participate in the extension study, consent may be obtained prior to, as part of, or after Visit 5 (no later than within 48 hours) of the Parent study. Subject eligibility will be established on the Enrollment Day which may be on the same day as the final visit (Visit 5) of the Parent study after the subject has exited the Parent study or no later than within 48 hours of exiting the Parent Study. If a subject was assessed to have met additional treatment criteria at Visit 5 of the Parent study, data of the additional treatment given will be collected at Enrollment Day.

Ideally, Enrollment Day assessments should occur on the same day as Visit 5 of the Parent study especially for those subjects who met additional therapy criteria at Visit 5 of the Parent study and were administered additional therapy, so that post therapy assessments may be performed as part of this extension study's Enrollment Day. If due to time constraints, it is not possible to conduct post therapy assessments on the same day as the injection of the additional therapy after exiting Visit 5 of the Parent study, the assessments should occur no later than within 48 hours of exiting the Parent study at Visit 5.

Additional safety follow-up visits will occur approximately every 4 weeks through Week 24 (Visits 6, 7 and 8; Weeks 16, 20 and 24, respectively). At Visits 6, 7 and 8 subjects will be evaluated to determine any need for additional treatment based on pre-defined criteria (Section 9.4.1).

If the subject's study eye qualifies for additional therapy at the final visit (Visit 5) of the Parent study or Visits 6 or 7 (Weeks 16 or 20) and receives additional therapy as a result, then ocular safety will be assessed in the study eye only following administration of the additional therapy.

The final visit of the extension study occurs at Visit 8 (Week 24). If the subject's study eye qualifies for additional therapy at the final visit (Visit 8) of the extension study and receives additional therapy as a result, data of the treatment administered will be collected whenever possible.

Intraocular pressure will be collected in both eyes at all visits during the extension study. Data from other ocular assessments at Visits 6 and 7 (Weeks 16 and 20) will be collected for the study eye only. All ocular assessments at Visit 8 (Week 24) will be performed on both eyes. Ocular assessment performed after the administration of additional therapy after exiting the Parent study at Visit 5 (Week 12) or Visits 6 and 7 (Weeks 16 and 20) of this extension study will be collected for the study eye only.

8.4.2. Enrollment Day (0 – 48 hours post Visit 5)

Subject eligibility will be determined on the Enrollment Day which will be the same day as the final visit (Visit 5) of the Parent study after the subject has exited the Parent study or no later than within 48 hours of exiting the Parent Study.

1. Written informed consent will be documented for each subject before any study-specific assessments are performed. To ensure subjects have adequate time to evaluate and provide informed consent to participate in the extension study, consent may be obtained prior to, as part of, or after Visit 5 (no later than 48 hours) of the Parent study.
2. Confirm subject meets all the inclusion and none of the exclusion criteria.
3. Confirm study eye (Section 9.2).
4. Collect urine and perform pregnancy test in females of childbearing potential.

Subjects satisfying the additional therapy criteria at the final visit (Visit 5) of the Parent study may receive additional therapy in the study eye. Data of therapy administered will be collected.

8.4.2.1. Enrollment Day - Additional Therapy

If the subject's study eye qualifies for additional therapy at the final visit (Visit 5) of the Parent study, then additional therapy, consisting of an [REDACTED]

8.4.2.2. Enrollment Day - Post Administration of Additional Therapy

The following assessments must be performed on the study eye after administration of additional therapy if the subject's study eye qualifies for additional therapy at the final visit (Visit 5) of the Parent study and receives additional therapy as a result.

1. Assess adverse events (AEs).

2. Review changes to concomitant medications.
3. Perform ophthalmic assessments on the study eye only:

4. Schedule time for subject to return for the next visit.

8.4.3. Visits 6 and 7 (Weeks 16 and 20)

At Visit 6 (Week 16) and Visit 7 (Week 20) additional therapy may be administered in the study eye only as needed based on pre-defined criteria described in Section 9.4.1 after the following procedures have been performed.

1. Confirm the study eye (Section 9.2).
2. Assess AEs.
3. Review changes in medical and ocular history.
4. Review changes to medications.
5. Obtain vital signs by performing resting heart rate (resting 5 minutes) and blood pressure measurements.
6. Perform ophthalmic assessments on the study eye only, unless otherwise designated:

7. Perform photographic evaluations on the study eye only: *

8. Determine if the subject's study eye qualifies for the additional therapy according to the Additional Therapy Criteria listed in Section 9.4.1. If the pre-defined criteria are met, then additional therapy consisting of

NOTE:

* All images (SD-OCT, fundus photographs and fluorescein angiography) should be uploaded to the Central Reading Center.

8.4.3.1. Visits 6 and 7 (Weeks 16 and 20) - Additional Therapy

If the subject's study eye qualifies for additional therapy according to the Additional Therapy Criteria listed in Section 9.4.1, then additional therapy, consisting of [REDACTED]

8.4.3.2. Visits 6 and 7 (Weeks 16 and 20) - Post Administration of Additional Therapy

The following assessments must be performed on the study eye after administration of additional therapy if the subject's study eye met Additional Therapy Criteria listed in Section 9.4.1 and receives additional therapy as a result.

1. Assess AEs.
2. Review changes to concomitant medications.
3. Perform ophthalmic assessments on the study eye only:

[REDACTED]
[REDACTED]
[REDACTED]
[REDACTED]

4. Schedule time for subject to return for the next visit.

8.4.4. Visit 8 (Week 24) End of Study/Early Termination

Visit 8 (Week 24) is the final study visit. Subjects who prematurely discontinue from the study should also complete all Visit 8 assessments.

1. Confirm study eye (Section 9.2).
2. Assess AEs.
3. Review changes to concomitant medications.
4. Obtain vital signs by performing [REDACTED]
[REDACTED]
5. Assess for changes to medical and ocular history.
6. Perform a review of body systems.
7. Collect urine and perform pregnancy test in females of childbearing potential.
8. Perform ophthalmic assessments on both eyes:

9. Perform photographic evaluations on both eyes:

10. Determine if the subject's study eye qualifies for the additional therapy according to the Additional Therapy Criteria listed in Section 9.4.1. Subjects satisfying the additional therapy criteria at Visit 8 (Week 24) will complete all Visit 8 assessments per protocol, exit the study and revert to standard of care as determined by the Investigator. Data of the additional therapy administered will be collected whenever possible. Subjects will then be released to the physician's care.

NOTE:

8.4.5. Unscheduled Visits

To ensure subject safety during the study, any subject who requires additional follow-up or treatment for any reason at any time during the study that does not fall on a scheduled study visit should have that visit recorded as an Unscheduled Visit, unless the visit results in study discontinuation at which point an attempt should be made to collect all Visit 8 assessments and the visit documented as such.

9. TREATMENT OF SUBJECTS

9.1. Treatment Regimen, Dosing, and Duration

No study drug will be dispensed or administered as part of this non-interventional extension study (Section 7.1).

9.2. Study Eye Determination

The study eye will be the study eye designated within the Parent study as having received CLS-AX at Visit 2 (Baseline, Day 1) of the Parent study and confirmed at subsequent visits including Visit 5 (Week 12, Study Exit) of the Parent study.

9.3. Fellow Eye Treatment

Subjects may have bilateral nAMD, but only the study eye from the parent study will continue enrollment into this extension study.

9.4. Additional Treatment

If, at any time during the study, a subject is considered at immediate risk for a vision-threatening event, then the Investigator should immediately follow best medical practice in the Investigator's judgement for treating the subject. All additional therapy will be recorded in the subject's source document(s) and the CRF.

9.4.1. Additional Therapy Criteria

At Visit 6 (Week 16), Visit 7 (Week 20) and Visit 8 (Week 24) of this extension study, subjects will be evaluated for the need for additional therapy for nAMD in the study eye based on the following criteria:

- 
- 
- 

If the pre-defined criteria are met at Visits 6 and/or 7 (Weeks 16 and/or 20), then additional therapy consisting of an IVT injection of aflibercept 2 mg (0.05 mL), ranibizumab 0.5 mg (0.05 mL), bevacizumab 1.25 mg (0.05 mL), or brolucizumab 6 mg (0.05 mL), as determined by the Investigator, may be administered; even if additional therapy is given, the subjects will remain in the study and will be followed until Visit 8 (Study Exit). Subjects satisfying the additional therapy criteria at Visit 8 (Study Exit) will complete all Visit 8 assessments per protocol, exit the study and revert to standard of care as determined by the Investigator. Data of the additional therapy administered will be collected whenever possible.

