3. Subjects of childbearing potential must agree to use acceptable methods of contraception throughout participation in the study. Acceptable methods of contraception include double barrier methods (condom with spermicide or diaphragm with spermicide), hormonal methods (oral contraceptives, implantable, transdermal, or injectable contraceptives), or an intrauterine contraceptive device with a documented failure rate of less than 1% per year. Abstinence may be considered an acceptable method of contraception at the discretion of the Investigator, but the subject must agree to use one of the acceptable birth control methods if he or she becomes sexually active. Females of childbearing potential must consent to performance of a pregnancy test.

Exclusion criteria:

Subjects are ineligible for participation in this study if s/he meets any of the following criteria:

1. [REDACTED]
2. Enrolled in the Parent study CLS1002-101 as part of Cohort 1.
3. Females of childbearing potential who are pregnant and or lactating.

Investigational product, dosage, and mode of administration:

No investigational product will be administered in this study.

Reference therapy, dosage, and mode of administration: None.

Criteria for evaluation:

Primary: Number of subjects experiencing adverse events and serious adverse events, grouped by organ class and preferred term, relatedness to study treatment, and severity.

Secondary: Incidence/descriptive statistics of changes in ocular safety parameters, visual function and ocular anatomy, and the need for additional treatment for nAMD.

Statistical methods:

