This is an open-label, non-interventional, extension study and therefore, no formal statistical testing of the endpoints will be conducted. The observed and change from baseline values will be summarized descriptively for each cohort. Categorical variables will be summarized by counts and percentages and continuous variables by descriptive statistics (n, mean, standard deviation, standard error, median, minimum, and maximum). Baseline is defined as the last assessment prior to administration of CLS-AX at Visit 2 (Day 1) in the Parent study. The Safety Population will include all enrolled subjects who are administered CLS-AX in the Parent study, and from whom at least one post-Enrollment Day visit safety measurement is obtained. The analysis will include all subject data collected in the Parent and extension studies for all subjects included in the Safety Population and will be limited to the endpoints collected in this extension study.

Sample size is not statistically driven as this is an extension study of [REDACTED]

Study Suspension:

The study enrollment will be immediately suspended, and no additional subjects will be enrolled upon suspension of the Parent study.

If the clinical study is suspended, the Sponsor will inform the Investigators and the regulatory authorities of the suspension and the reason(s) for the suspension. The Investigator should promptly notify the Institutional Review Board (IRB) or Independent Ethics Committee (IEC) of the suspension and of the reasons.

Enrollment of subjects into the study will not be restarted until the Sponsor and the Safety Monitoring Committee have agreed to the course of action to be taken in the Parent study and the IRB /IEC has been notified.

During the period of suspension of enrollment, provided the Investigator determines that it is in the subjects' best interest to continue in the study, subjects currently enrolled in the extension study will continue with the protocol specified visit schedule. The Sponsor's preference is to retain enrolled subjects in the extension study until the final study visit (Visit 8, Week 24).

Additional therapy criteria:

Subjects will be assessed for [REDACTED]

[REDACTED]

[REDACTED]

[REDACTED]

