Results from Cohort 1 of the open label, dose-escalation Parent study, CLS1002-101, support the rationale for conducting an extension of follow-up of subjects receiving CLS-AX in cohorts 2, 3 and 4. A total of 6 subjects were enrolled into Cohort 1 of the Parent study. Of these subjects, 2 subjects completed the study without meeting the pre-specified criteria for the administration of additional therapy, demonstrating at least 3 months durability of the effect of CLS-AX on BCVA and central subfield retinal thickness assessed via optical coherence tomography. Without longer follow-up, a more comprehensive assessment of durability will not be possible. Given the anticipated similar or longer durability of effect, a longer duration of follow-up is justified for cohorts 2, 3 and 4, to more fully assess long-term safety, tolerability and effects on visual function and ocular anatomy.

All subjects entering this trial will have received CLS-AX at Visit 2 (Baseline, Day 1) of the Parent study, CLS1002-101, as investigational product. The objective of the Parent study is to evaluate the safety and tolerability, over 12 weeks of follow-up, of a single dose of suprachoroidally administered CLS-AX in subjects with nAMD who show stable visual acuity following 3 or more injections with an intravitreal anti-VEGF therapy in the preceding 5 months.

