6.2. Secondary Objectives

To evaluate the effect of a single dose of CLS-AX on visual function and ocular anatomy and the need for additional treatment for symptoms of nAMD up to 24 weeks following administration of CLS-AX at Visit 2 (Baseline, Day 1) in the Parent study.

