12. STATISTICS

A detailed statistical analysis plan will be prepared for this study. The plan will contain a discussion of the statistical methods, a description of the computational algorithms, data handling conventions, and specifications for the data summaries and listings. It will be finalized before the last subject enrolled has completed the study.

The analysis will include all subject data collected in the Parent study and this extension study for all subjects included in the Safety Population (Section 12.4.1). Safety data to be summarized will be limited to the endpoints collected in this extension study.

[figure not shown]

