12.4. Analysis Populations

12.4.1. Safety Population

The Safety Population will include all subjects who are administered CLS-AX in the Parent study, who have provided informed consent for participating in the Extension study, and from whom at least one safety measurement is obtained after the subject has provided informed consent.

In the safety analysis, all subject data from both the Parent and extension studies will be used; no data will be excluded due to protocol deviations.

All safety analyses will be based on the Safety Population.

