12.5.3. Secondary Safety Analyses

Secondary safety analyses will be performed on all subjects in the Safety Population. Ocular safety will be assessed by evaluating IOP, BCVA and outcomes obtained from the slit-lamp biomicroscopy, indirect ophthalmoscopy, SD-OCT, fundus photography and angiography examinations. Summaries will be provided for each dose cohort for the Study eye.

Systemic safety will be assessed by evaluating vital signs and concomitant medications. Summaries will be provided for each dose cohort.

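### Week 16 to 24 BCVA and CST means can include study eyes already given additional anti-VEGF therapy, so on their own they do not describe the single-dose effect named in the secondary objective

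*Combined protocol and SAP*

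**What the plan says.** Section 6.2 gives the secondary objective: "To evaluate the effect of a single dose of CLS-AX on visual function and ocular anatomy and the need for additional treatment", to 24 weeks after the Parent-study injection. The Synopsis gives the matching criteria for evaluation as "Incidence/descriptive statistics of changes in ocular safety parameters, visual function and ocular anatomy, and the need for additional treatment for nAMD".

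Additional therapy can enter at three scheduled points before the last visit. Section 8.4.2 allows it for eyes that qualified at Parent Visit 5 (Week 12). Sections 8.4.3 and 9.4.1 allow it at Visits 6 and 7 (Weeks 16 and 20), once that visit's procedures are done. Section 9.4.1 then says that "even if additional therapy is given, the subjects will remain in the study and will be followed until Visit 8 (Study Exit". Sections 8.4.5 and 9.4 also leave room for treatment between scheduled visits.

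On analysis, the Synopsis says "The observed and change from baseline values will be summarized descriptively for each cohort". Section 12 says "The analysis will include all subject data collected in the Parent study and this extension study for all subjects included in the Safety Population". Section 12.5.3 lists BCVA and SD-OCT among the ocular safety outcomes and says "Summaries will be provided for each dose cohort for the Study eye". Section 12.5.4 plans no subgroup analyses.

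The current bullets of Section 7.2.2 are redacted. The only visible endpoint wording is the changed-to column for that section in the Amendment 1 summary of changes. It lists mean change in BCVA and in CST, and numbers and percentages of subjects qualifying for or receiving additional therapy, each at Visits 3 to 8.

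**The concern.** The objective asks what one dose of CLS-AX does up to Week 24. Once an eye has had an anti-VEGF injection, its later BCVA and CST reflect that injection as well. A cohort mean that pools such eyes with untreated ones does not show how much belongs to CLS-AX. Section 12.5.1 plans comparisons between dose cohorts, and these are hard to read if the cohorts differ in how many eyes were treated.

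The Introduction also shows what the sponsor regards as evidence of durability. Two of the six Cohort 1 subjects finished the Parent study "without meeting the pre-specified criteria for the administration of additional therapy, demonstrating at least 3 months durability of the effect of CLS-AX", and this is offered as a reason for the extension. A reader will want the same kind of figure at Week 24. Counts at separate visits do not supply it.

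**Working it through.** **Which means can contain post-therapy values.** At Visits 6 and 7 therapy follows the assessments, so it affects the next visit's values and not the same visit's.

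| Mean at | Can include eyes treated at |
|---|---|
| Week 16 | Week 12 (Parent Visit 5) |
| Week 20 | Week 12 or 16 |
| Week 24 | Week 12, 16 or 20 |

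Therapy at an unscheduled visit could add to any row. Whether eyes treated in the Parent study before Visit 5 could enter cannot be checked, because exclusion criterion 1 is redacted.

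**The documents' own durability figure.** For Cohort 1 it is 2/6 = 33% (exact 95% interval 4% to 78%). The text does not say what happened to the other four subjects, so this is not a therapy rate to project onto Cohorts 2 to 4.

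**How far a mean could move (illustration).** One treated eye among n shifts the cohort mean by g/n, where g is the difference in that eye's value due to the therapy. The documents give no g, so assume 0, 3 or 10 letters.
- n = 5 (approximate cohort size, Section 12.2): 0/5 = 0, 3/5 = 0.6, 10/5 = 2.0 letters.
- n = 19/3 = 6.3 (maximum of 19 subjects split evenly, an assumption): 0, 3/6.33 = 0.5, 10/6.33 = 1.6 letters.

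The direction is also open. Treated eyes may have gained from the therapy, or they may be the eyes doing worse.

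**What counts at each visit say about eyes ever in need.** If each visit gives only a count, the number of distinct eyes lies between max(counts) and min(n, sum of counts).
- Counts 2, 2, 2 at Weeks 16, 20 and 24 with n = 5: max = 2 and min(5, 6) = 5, so 2 to 5 eyes (40% to 100%).
- Counts 1, 1, 1 with n = 5: 1 to min(5, 3) = 3 eyes.
- One eye at each of the six listed visits with n = 5: 1 to min(5, 6) = 5 eyes.
- Counts of 0, 0, 0, or 5 of 5 at any visit, leave no ambiguity over the visits counted.

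These bounds need no assumption about effect size, but they do depend on reading the endpoint as separate counts at each visit.

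**The case against.** The strongest reply is that much of this is unseen, not absent. The Section 7.2.2 bullets are redacted. Section 12 leaves data-handling conventions and the specification of summaries and listings to a separate SAP, and Section 12.5 leaves further endpoints to it. That stands: the finding is that no visible text covers the matter.

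Four stronger readings are tempting, and the documents do not support them.

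- *The plan counts need for therapy only visit by visit.* That is the natural reading of the changed-to wording, but an any-visit count is not strictly excluded, and the Synopsis speaks of incidence.
- *The plan abandons a durability endpoint it had defined.* The Introduction's sentence is rationale, not an endpoint definition, and its criterion is still counted at visits.
- *Additional therapy goes unreported.* Section 10 records it as concomitant or rescue medication, and Section 12.5.3 summarises concomitant medications by cohort. With about five eyes per cohort, listings might also show each eye's history. But no visible text links the therapy to the BCVA and CST means.
- *The all-data summary is wrong, or flatters CLS-AX.* For safety, Section 12.4.1 states: "all subject data from both the Parent and extension studies will be used; no data will be excluded due to protocol deviations". That suits the primary safety objective. Nothing in the documents gives the direction of any distortion.

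It is also fair to say that no summary here can isolate a CLS-AX effect. There is no control group, and Section 7.1 has aflibercept given at Screening.

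**Conclusion.** The point holds as an inexpensive improvement of minor to moderate weight, confined to a descriptive secondary objective for which Section 12.2 plans no formal testing. Read as written, the visible plan lets Week 16, 20 and 24 BCVA and CST means mix eyes with and without later anti-VEGF therapy and does not say how that will be shown. If need for therapy is counted separately at each visit, the counts do not fix how many eyes ever needed it.

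This rests on the changed-to wording standing for the redacted bullets, and on the unsupplied SAP not already containing a rule. The number of treated eyes in Cohorts 2 to 4, and the size and direction of any effect on the means, are unknown. The letter shifts above are illustrations only.

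**What to change.** In Section 12.5.3 and the SAP, or by cross-reference if the SAP already does this:

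1. Keep the all-data summary as safety, and print beside each Week 16, 20 and 24 mean the number of study eyes previously given additional therapy.
2. Add, by cohort, the cumulative number and proportion of study eyes that have first qualified for or first received additional therapy at any scheduled or unscheduled visit, with time from Day 1. At Visit 8 use qualification, because Section 8.4.4 collects receipt only where possible. Count exit because of additional therapy as an event. State that the summary covers only Parent completers who entered the extension.
3. Add a BCVA and CST summary restricted to values up to the last measurement before first additional therapy, with n at each visit, labelled descriptive.

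Settle this before the first cohort is analysed, since Section 12.5.1 analyses the open-label cohorts in sequence.

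The cost is some wording and two or three tables, with no new assessments. BCVA is measured at Visits 6, 7 and 8 (Section 11.1.1), and additional therapy goes on the CRF (Section 9.4). Confirm that the CRF holds the therapy date and that Parent Visit 5 measurements precede therapy. The drawback is imprecision and selection. An exact 95% interval for 2/5 runs from 5% to 85%, and late pre-therapy means will rest on a few selected eyes. The tables describe durability and do not establish a causal effect.

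Separately, Section 8.3 allows removal of subjects who require additional therapy, while Section 9.4.1 keeps them to Visit 8. These passages must be reconciled, because the answer determines which eyes contribute to the later means.
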